9.5.4 Safety Evaluation

In general, safety data will be provided in listings by study arm, site, patient, visit and time-point if applicable. The data will be tabulated on the Safety Set by study arms and in patients exposed but not randomized.

Item name	Definitions
Adverse Event (AE)	Adverse event is any unfavorable and unintended sign (including a clinically significant abnormal laboratory finding), symptom, or disease temporally associated with the use of an IP, whether or not it is considered related to the IP.

Confidentiality Statement

Data and information contained in this document are considered to constitute trade secrets and confidential commercial information, and the legal protections provided to such trade secrets and confidential information are hereby claimed under the provisions of applicable law. No part of this document may be publicly disclosed without the written consent of Philip Morris Products S.A

Item name	Definitions
	Worsening of the AAA parameters (maximum minor-axis AAA diameter in mm, AAA annual growth rate, maximum minor-axis AAA diameter growth of above 5 mm in 6 months) will not be considered as an AE.
Serious Adverse Event (SAE)	An SAE is defined as, but not limited to, any untoward medical occurrence that: 
• Results in death.• Is life-threatening.• Requires inpatient hospitalization or prolongation of existing hospitalization.• Results in persistent or significant disability/incapacity,• Is a congenital anomaly/birth defect, or• Is an important medical event.

9.5.4.1 Adverse Events

AEs will be summarized by both the number and percentage of patients experiencing an event and the number of events experienced during the study period by Medical Dictionary for Regulatory Activities (MedDRA) System Organ Class (SOC) - sorted by alphabetical order, Preferred Terms (PT) - sorted by alphabetical order.

If a subject has AEs that occurs and resolves on multiple occasions, each AE is counted once at each severity. Unless otherwise noted, target population will be used as denominator for frequency table.

AEs will be summarized by study arm, SOC and PT.

Confidentiality Statement

Data and information contained in this document are considered to constitute trade secrets and confidential commercial information, and the legal protections provided to such trade secrets and confidential information are hereby claimed under the provisions of applicable law. No part of this document may be publicly disclosed without the written consent of Philip Morris Products S.A

Adverse Events														
Population	:	Safety Set												
Group	:	Study Arm												
		
• The number and percentage of patients experiencing an adverse event and the number of adverse events during the study period.• The “Overview of Adverse Events” includes a summary of the following items
➢ Subjects with at least one AE and number of AEs➢ Subjects with at least one SAE and number of SAE. And criteria of seriousness.➢ AE severity➢ Relation to study procedure or investigational product➢ Smoking related disease➢ Co-morbidity➢ Action taken with the investigational product➢ Action taken in response to AE➢ Relation to SARS-CoV2												
Contents														
		
• The “Summary of Adverse Events” shows a tabulation of adverse events by SOC/PT.• Common Adverse Events are defined as AE that occurred at least 5% of the subjects in any of the study arms.• The “Annual summary of Adverse Events” shows a tabulation of adverse events by SOC/PT in each year after the enrollment. AE will be summarized based on the study day. Study Day= Date of AE occurred - randomization date + 1												
		

Year	Study Day	

Before Randomization	< 0	

0 < \leq 1	1 \leq \leq 365	

1 < \leq 2	365 < \leq 730	

2 < \leq 3	730 < \leq 1095	

3 <	1095 <	

	Year	Study Day	Before Randomization	< 0	0 < \leq 1	1 \leq \leq 365	1 < \leq 2	365 < \leq 730	2 < \leq 3	730 < \leq 1095	3 <	1095 <
Year	Study Day													
Before Randomization	< 0													
0 < \leq 1	1 \leq \leq 365													
1 < \leq 2	365 < \leq 730													
2 < \leq 3	730 < \leq 1095													
3 <	1095 <													
Output	:	Overview of Adverse Events -Safety Set- Summary of Adverse Events -Safety Set-												

Confidentiality Statement

Data and information contained in this document are considered to constitute trade secrets and confidential commercial information, and the legal protections provided to such trade secrets and confidential information are hereby claimed under the provisions of applicable law. No part of this document may be publicly disclosed without the written consent of Philip Morris Products S.A

		Summary of Common Adverse Events -Safety Set- Summary of Non-serious Common Adverse Events -Safety Set- Annual Summary of Adverse Events -Safety Set- Listing of Adverse Events
--	--	--

Adverse Events by Severity		
Population	:	Safety Set
Group		Study Arm
Contents	:	
• The number and percentage of patients experiencing an adverse event and the number of adverse events during the study period by severity. If a subject experiences the same adverse event at more than one severity, then the AE will be counted (in the Table) at each severity where it appears.• Any missing severity will be accounted as “severe”.
Output		Summary of Adverse Events by Severity -Safety Set-

Expectedness of Adverse Events Related to Investigational Product		
Population	:	Safety Set
Group		Study Arm (Only IQOS and CIG)
Contents	:	The number and percentage of patients experiencing an adverse event related to an investigational product and its expectedness (Yes/No). Yes=expected, No=unexpected.
Output		Summary for Expectedness of Adverse Events Related to Investigational Product -Safety Set-

Confidentiality Statement

Data and information contained in this document are considered to constitute trade secrets and confidential commercial information, and the legal protections provided to such trade secrets and confidential information are hereby claimed under the provisions of applicable law. No part of this document may be publicly disclosed without the written consent of Philip Morris Products S.A

Relatedness of Adverse Events to Study Procedure		
Population	:	Safety Set
Group		Study Arm
Contents	:	The number and percentage of patients experiencing an adverse event related to study procedures.
Output		Summary for Relatedness of Adverse Events Related to Study Procedure -Safety Set-

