4.3 Study Duration

The study duration for each patient will be up to 3 years and 1 month. This includes the Screening Period of up to 28 days prior to Visit 2 (Baseline Visit), followed by an Investigational Period up to 3 years.

The end of the study for an individual patient will be defined as V8 or the date of early termination. The end of the entire study is the latest date that an individual patient reaches the end of the study.

Confidentiality Statement

Data and information contained in this document are considered to constitute trade secrets and confidential commercial information, and the legal protections provided to such trade secrets and confidential information are hereby claimed under the applicable provisions of applicable law. No part of this document may be publicly disclosed without the written consent of Philip Morris Products S.A.

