8.2.1 Assessment of Adverse Events

Adverse event information will be collected from the time of signature of the ICF onwards until the end of Investigational Period either by the Investigator via spontaneous reporting or by the use of consistent, open, non-directive questions from study site collaborators (e.g., “Have you had any health problems since the previous visit/How have you been feeling since you were last asked?”). The main source for AE collection will be face-to-face interview(s) with the patient.

Information recorded will include: verbatim description of the AE, start and stop dates and times, seriousness, severity (intensity), action taken (e.g., whether or not the AE led to the patient’s discontinuation from the study), and outcome (e.g., resolved, discontinuation due to AE).

For each AE, the intensity (severity) will be graded on a 3-point intensity scale (mild, moderate, severe) using the definitions provided in Section 8.2.3.

Any exacerbation/worsening of an AE or pre-existing condition shall be evaluated and recorded.

Correct medical terminology/concepts are preferred when recording AE terms, and abbreviations must be avoided. Wherever possible, a diagnosis is to be used to describe an AE rather than individual signs and symptoms (e.g., record ‘pneumonia’ rather than ‘fever,’ ‘cough,’ ‘pulmonary infiltrate,’ or ‘septicemia,’ rather than ‘fever’ and ‘hypotension’ following blood sample).

Any AE that meets the serious criteria must be recorded both on the AE report form of the CRF and on a separate SAE report form (Section 8.3).

Information regarding AEs related to product events should be actively collected during the study visits.

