8.2.2 Period of Collection

Any AEs (including SAEs) will be captured by the study site collaborators and assessed by the Investigator(s) or designee(s) in order to establish relationship to IP and study procedures. AEs (including SAEs) will be collected from the time the patients have signed their ICFs until the end of the Investigational Period.

All collected AEs will be reported in the clinical study report (CSR) as described below and in accordance with the respective local regulatory guidelines.

Confidentiality Statement

Data and information contained in this document are considered to constitute trade secrets and confidential commercial information, and the legal protections provided to such trade secrets and confidential information are hereby claimed under the applicable provisions of applicable law. No part of this document may be publicly disclosed without the written consent of Philip Morris Products S.A.

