8.2.2.1 Screening Period

All existing health conditions identified during the Screening Visit and judged by the Investigator as a preexisting condition will be recorded as concomitant disease and the patient's eligibility for admission to the study will be reviewed. Any AEs which occur during the Screening period will be captured by the study site staff and assessed by the Investigator(s) or designee(s) in order to establish relationship or relatedness in respect to study procedures. For screen failure patients, only the study procedure-related AEs will be reported in the CRF and in accordance with respective regulatory guidelines.

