Data and information contained in this document are considered to constitute trade secrets and confidential commercial information, and the legal protections provided to such trade secrets and confidential information are hereby claimed under the applicable provisions of applicable law. No part of this document may be publicly disclosed without the written consent of Philip Morris Products S.A.

Time	Sample collection	Procedures	Additional information
Start of procedure			
		Clinical assessments:	
		Vital signs	Vital signs: at least 15 min after having smoked CC or used IQOS. Systolic and diastolic blood pressure also assessed as cardiovascular risk factors
		Physical examinations	
		Body weight	Assessed as cardiovascular risk factor
		Waist circumference	Assessed as cardiovascular risk factor
		AE/SAE recording	
		Debriefing on IQOS	Smoking patients only.
		Randomization	Smoking patients only
		Patients are informed of their randomized study arm.	Smoking patients only
		Distribution of the IQOS supplies as per site process	Smoking patients randomized to IQOS arm only
		Any other assessment as per standard of care for AAA patients and deemed necessary by the Investigator	
End of the visit			
After check out		Patients start using their allocated product	IQOS and CC arm only

Abbreviations: AAA = Abdominal Aortic Aneurysm; AE = Adverse event; ; B = Blood/Plasma; CEMA = 2-Cyanoethylmercapturic Acid; CT = Computed Tomography; NEQ = nicotine equivalents, consisting of the molar sum of free nicotine, nicotine-glucuronide, free cotinine, cotinine-glucuronide, free trans-3'-hydroxycotinine and trans-3'-hydroxycotinineglucuronide; NNAL = 4-[methylnitrosamino]-1-[3-pyridyl]-1-butanol; NNN = N-nitrosonornicotine; SAE = Serious adverse event; SC = Smoking Cessation; U = Urine; .

Confidentiality Statement

Data and information contained in this document are considered to constitute trade secrets and confidential commercial information, and the legal protections provided to such trade secrets and confidential information are hereby claimed under the applicable provisions of applicable law. No part of this document may be publicly disclosed without the written consent of Philip Morris Products S.A.

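### Apart from the annual summary, the by-arm adverse event tables do not separate events before V2, so cigarette-period events of future IQOS patients appear in the IQOS column

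*SAP*

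**What the plan says.** **Collection.** Protocol 8.2.1 states: "Adverse event information will be collected from the time of signature of the ICF onwards until the end of Investigational Period". Section 8.2.2.1 adds: "Any AEs which occur during the Screening period will be captured by the study site staff". Section 4.3 counts up to 28 days of screening as part of the study duration.

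**Product in use.** Under Protocol 6.2.1, smokers may carry on with their usual cigarettes between V1 and V2. Table 5 in Protocol 9.2 places the line "Patients start using their allocated product" after check-out from V2, and it lists adverse event recording ahead of randomisation on the same day.

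**Tabulation.** SAP 9.5.4.1 says: "AEs will be summarized by study arm, SOC and PT". The contents are "The number and percentage of patients experiencing an adverse event and the number of adverse events during the study period", with no start date and no treatment-emergent definition. The severity and SAE tables use the same window wording. The table of expectedness for product-related events gives no window at all.

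**The exception.** The annual summary in SAP 9.5.4.1 sorts events by a study day counted from randomisation and has a row for events before it.

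**The concern.** Adverse events are the primary safety assessment (Protocol 12.8), and the comparison of interest is IQOS against continued smoking. An event during screening cannot be an effect of the allocation. In the CIG and SC arms product use is not meant to change at V2, so a screening event at least sits under the right habit. In the IQOS arm it sits under a product that the patient had not yet been allocated.

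The SAP abbreviation list counts cigarettes as an investigational product. A screening event judged related to cigarettes could therefore enter the product-related expectedness table in the IQOS column. With few patients, a reader of the overview or SOC/PT table cannot tell such events from events on IQOS.

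**Working it through.** The plan gives no event rate or arm-level figure on this point, so there is nothing to reproduce. The check has four steps.

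**1. Are pre-V2 events in the tables?** The SAP does not say when its study period starts. Two things point to consent: the protocol's collection period, and the annual table's row for events before randomisation, which would be empty by design if counting began at V2.

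**2. Share of observation time.** Screening is at most 28 days (Protocol 4.3).
- Completer: 3 × 365.25 ≈ 1,096 days, so 28/(28 + 1,096) = 28/1,124 = 2.5%.
- Leaving at month 6: 0.5 × 365.25 ≈ 183 days, so 28/(28 + 183) = 28/211 = 13.3%.

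**3. Effect on the randomised comparison.** Assume constant rates: λ on cigarettes and rλ on IQOS. Let T be the years after V2 and s = 28/365.25 = 0.0767. Both arms have rate λ in screening.
- Difference in expected counts per patient: (λs + rλT) − (λs + λT) = (r − 1)λT. Screening cancels.
- Rate ratio with screening pooled: (rT + s)/(T + s). The base rate λ cancels.

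| True ratio r | T = 3 years | T = 1 year | T = 0.5 years |
|---|---|---|---|
| 0.50 | 0.51 | 0.54 | 0.57 |
| 2.00 | 1.98 | 1.93 | 1.87 |

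The ratio moves slightly toward 1, whichever arm has the higher rate.

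**4. Chance in small arms.** Protocol 4.4 reports 32 patients enrolled when the decision to stop recruitment was made, and a forecast of 15 more. Neither document gives final numbers per arm. Assuming three equal arms, 32/3 = 10.7 and (32 + 15)/3 = 15.7, so I take 10 to 16 per arm. One patient whose only event fell in screening then adds 1/16 = 6 to 1/10 = 10 percentage points to that arm.

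**The annual table.** Study day is event date minus randomisation date plus 1.
- The day before randomisation: −1 + 1 = 0. The rows are below 0 and 1 to 365, so day 0 has no row.
- The randomisation day: 0 + 1 = 1. This falls in year 1, even for an event before check-out.
- SC patients are enrolled without randomisation (Protocol 6.4.2, SAP 4.3.1.2), so they have no reference date, although the table is described as counting years from enrolment.

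**The case against.** The strongest reply is that the problem is small and partly handled.

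- The annual summary already shows pre-randomisation events by arm, SOC and PT, and a listing is planned. This stands, subject to the two defects shown above. It does not help a reader of the other tables.
- Few screening events should arise. Conditions found at the Screening Visit and judged pre-existing are recorded as concomitant disease (Protocol 8.2.2.1). Acute severe cardiovascular or respiratory events within 3 months are exclusionary and re-checked at V2 (exclusion criterion 2). This also stands.
- Product relatedness may be protected, because Protocol 8.2.2.1 has screening events assessed against study procedures. Section 8.2.2 names the investigational product as well, so the protection is not certain.
- The study is descriptive, with no hypothesis to test. True, but in such a study the tables are the result.

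A reader might infer a bias against IQOS, because only that arm changes product at V2. The documents do not support this. Both randomised arms come from one pool of smokers, allocated 1:1 within strata, so screening events are equal in expectation.

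A reader might also infer that every adverse event table counts from consent. The discontinuation, expectedness and procedure-relatedness tables do not carry the study-period wording. Patients can be discontinued only after enrolment (Protocol 5.2), and a death in screening never reaches the Safety Set, so the death and discontinuation tables are barely touched.

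Finally, the common-event rule, "Common Adverse Events are defined as AE that occurred at least 5% of the subjects in any of the study arms", is met by one patient in any arm of 20 or fewer (1/20 = 5%). That holds equally for an event after V2, so it reflects arm size and not this gap.

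**Conclusion.** The point holds in a limited form. Outside the annual summary, the overview, SOC/PT, common, severity, product-related expectedness and SAE tables do not separate events with onset between consent and V2. A future IQOS patient's event while still smoking is therefore shown under IQOS.

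The consequence is slight dilution: at most about 2.5% of a completer's time, and about 13% for a patient leaving at month 6. Chance noise in small arms comes on top.

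This rests on four assumptions:
- The study period starts at consent. This is a well-supported inference, not SAP wording.
- Rates are constant, for the dilution figures.
- Arms have 10 to 16 patients, for the noise figure.
- Future IQOS patients use cigarettes until V2. Exclusion criterion 8 bars only daily use of heated tobacco or tobacco vapor products, so occasional earlier use is possible.

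The balance argument covers only the two randomised arms, not comparisons with SC. The gap is worth closing because the tables mislabel exposure and the correction is cheap. It is unlikely to change the overall safety reading.

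**What to change.** In SAP 9.5.4.1:
- Base the overview, SOC/PT, common, severity, product-related expectedness and SAE tables on events that start or worsen after V2 allocation or first use of the allocated product (SC: after V2 enrolment). Choose one cut and state it. Protocol 8.2.1 records start times as well as dates, so events earlier on the V2 day can be sorted where the time is known.
- Show events from consent to V2 once, in a separate pre-allocation column or table, and in the listing.
- Keep screening events in the procedure-relatedness table. The V1 scan, X-ray and blood draw are study procedures, and Protocol 8.2.2.1 asks for that attribution.
- In the annual table, assign study day 0 to the row before randomisation, and use the V2 enrolment date for SC patients.

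The cost is one analysis flag, one small table and slightly lower headline counts. No new data are needed, and no event disappears from the report.

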4.3.1.2 SC Arm

Patients who had stopped smoking will be enrolled in the SC arm at Baseline Visit (V2) through the Interactive Web and Voice Response System (IXRS) without being randomized.

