9.5.2.1.2 Rupture or Surgical Treatment of AAA

Annual Incidence Rate of AAA Rupture, Open Surgical Treatment, Endovascular Repair

Population	:	FAS
Group	:	
• Study Arm• Product Use Category
Contents		
• Count the number of patients for the following variables
➢ Open surgical AAA treatment or AAA endovascular repair➢ AAA rupture
Definitions		
Number of patients were calculated by person-year-method: number of patients event occurred / (sum of days until event occurred / 365.25).
 
Days until event occurred is as follows:
 
 Date of decision to perform open surgical AAA treatment or AAA endovascular repair - randomization date + 1.
 
 Date of AAA rupture - randomization date + 1.
 
 For those without experiencing the event.
 
 Subject Reference End Date - randomization date + 1.

Output	:	
Annual Incidence Rate of AAA Rupture, Open Surgical Treatment, Endovascular Repair -FAS-
 
Annual Incidence Rate of AAA Rupture, Open Surgical Treatment or Endovascular Repair by Product Use Category -FAS-
 
Listing of Patients Annually Undergoing AAA Rupture, Open Surgical Treatment, Endovascular Repair

Confidentiality Statement

Data and information contained in this document are considered to constitute trade secrets and confidential commercial information, and the legal protections provided to such trade secrets and confidential information are hereby claimed under the provisions of applicable law. No part of this document may be publicly disclosed without the written consent of Philip Morris Products S.A.

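### The incidence rates and the annual adverse event table count time from a randomization date that SC patients do not have, and the annual table has no row for study day 0

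*SAP*

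**What the plan says.** SAP 9.5.4.1 describes the annual summary as a "tabulation of adverse events by SOC/PT in each year after the enrollment". The same bullet then gives the rule "Study Day= Date of AE occurred - randomization date + 1". The first row of its year table is "Before Randomization < 0", and the next row covers days 1 to 365.

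SAP 9.5.2.1.2 defines the repair and rupture rates as "number of patients event occurred / (sum of days until event occurred / 365.25"). The days run from randomization in every case. For rupture the rule is "Date of AAA rupture - randomization date + 1", and for patients without the event it is "Subject Reference End Date - randomization date + 1". The repair rule has the same form, using the date of the decision to operate.

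The outputs in 9.5.2.1.2 are grouped by study arm and by product use category, and those in 9.5.4.1 by study arm. SAP 4.3.1.2 says that SC patients enter at V2 "through the Interactive Web and Voice Response System (IXRS) without being randomized". Protocol 6.4.2 says the same.

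**The concern.** A formula that subtracts a randomization date has no value for a patient who was never randomized. Neither section gives a substitute date for SC.

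Both outputs are meant to include SC. Secondary objective 2 compares repair and rupture with patients who had stopped smoking, and objective 4 covers safety under smoking cessation. Where the SAP wants an arm left out, it says so: the expectedness table is limited to IQOS and CIG, and the device table to IQOS. Neither limit appears here.

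Two things are at stake: the SC rates and annual adverse event counts, and the incidence rate in any product use category that mixes SC with randomized patients. The day-0 gap is a second, smaller defect confined to the annual adverse event table, since the incidence rates have no day bins.

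**Working it through.** The plan gives no figure to reproduce, so the check applies its rules as written.

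**Inputs.** Formulas and bins come from SAP 9.5.2.1.2 and 9.5.4.1. SC allocation comes from SAP 4.3.1.2. Screening is Day -28 to Day -1 and V2 is Day 1 (Protocol section 4 and Appendix 1). Adverse events are collected from signature of consent (Protocol 8.2.2). The SC arm size is not given; Protocol 4.4 reports only 32 patients enrolled in total at the time of the amendment. I therefore assume 5, 10 or 15 SC patients with 1096 days of follow-up each.

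**1. SC person-time.** Person-years = sum of (end date - randomization date + 1) / 365.25. With the randomization date missing, no SC patient has a term in the sum. With V2 enrolment as origin:

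| SC patients (assumed) | As written | V2 origin |
|---|---|---|
| 5 | none | 5 × 1096 / 365.25 = 15.0 |
| 10 | none | 10 × 1096 / 365.25 = 30.0 |
| 15 | none | 15 × 1096 / 365.25 = 45.0 |

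**2. Pooled product use category.** Under SAP 5.7, SC patients and randomized patients who stop using tobacco can share the abstinence category. Suppose it holds 10 SC and 2 randomized patients, with one event, in an SC patient. Suppose also that the program counts the event but skips missing times.

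- As written: 1 / (2 × 1096 / 365.25) = 1 / 6.00 = 0.167 per person-year.
- With V2 origin: 1 / (12 × 1096 / 365.25) = 1 / 36.01 = 0.028 per person-year.

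The first is six times the second. This is an illustration of the mechanism, not a forecast.

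**3. Day 0.** Let R be the randomization date.

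| Onset | Study day by the SAP formula | Row |
|---|---|---|
| R - 2 | -1 | before randomization |
| R - 1 | 0 | none |
| R | 1 | first year |

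Checking every date from 28 days before to 1199 days after R finds exactly one date with no row, R - 1, and no date with two rows. The protocol's Day -28 to Day -1 become SAP days -27 to 0. Because collection starts at consent, an event can begin on the unbinned day.

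**4. After correction.** Every date falls in exactly one row if the first row is day 0 or earlier, or if 1 is added only on or after R.

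**The case against.** The best defence is that the intended origin is evident. SAP 9.5.4.1 itself speaks of years after enrolment. SAP 9.1.4 takes V2 as baseline for SC. SAP 9.2 uses, as the denominator for disposition events, patients randomized to IQOS or CIG or enrolled in SC. SC enrolment goes through the same IXRS at the same visit as randomization, so an equivalent date exists for every SC patient. A programmer would be unlikely to leave the SC column blank.

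This stands as an account of intent. A reader might infer from the formulas that SC rates cannot be computed at all; these sections do not support that. But the written formulas contradict the intent, and 9.5.2.1.2 has no wording about enrolment, so there the inference rests wholly on other sections.

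A reader might also infer that adverse events are lost from the study. They are not: the overview, SOC/PT, severity, serious event, death and discontinuation tables and the listings do not use study day.

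Nor does 1 day in 28 (3.6%) give a usable share of pre-randomization events missed. It assumes uniform onset and a full screening period, which the protocol caps at 28 days. On the same assumption a 14-day screening gives 1/14 = 7.1% and a 7-day one 1/7 = 14.3%. The number of such events is not given and may be zero.

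Finally, patient counts by year need not sum to the overall count, because one patient can have events in several years. Only event counts should reconcile.

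**Conclusion.** The point holds as a minor defect in two stated rules. Followed literally, they leave the SC arm with no person-time in the repair and rupture rates and no study day in the annual adverse event table. They also allow a distorted rate where a product use category pools SC with randomized patients. The size depends on the SC arm size and on how missing dates are programmed, neither of which the documents give.

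Patients exposed but not randomized, whom SAP 8.2 and 9.5.4 include in the safety tabulations, have the same problem in the annual table. They do not enter the incidence rates, because the FAS is limited to randomized and SC patients.

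The day-0 gap is one calendar day per patient in one table, and the number of events affected is probably very small. The primary growth rate (study day from the baseline measurement, SAP 9.5.1.1) and the Kaplan-Meier analyses (from diagnosis, SAP 9.5.2.1.1) are untouched.

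**What to change.** In SAP 9.5.2.1.2 and 9.5.4.1, replace the randomization date with a reference date: the randomization date for IQOS and CIG, and the V2 enrolment date for SC and for patients exposed but not randomized.

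For the annual table, choose one of two corrections:

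- Make the first row study day 0 or earlier, labelled as before randomization or enrolment. This closes the gap but leaves SAP screening days one off from the protocol's.
- Add 1 only for dates on or after the reference date. This keeps the present bins and matches the protocol's numbering from Day -1 to Day 1. The row label should still mention enrolment.

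The cost is a few lines of SAP text and a small change to the derivation program. The dates are already collected. If the database is already locked, record the rule used in the clinical study report, as SAP section 1 provides for changes to the planned analyses.
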